7.3.2.5 Follow-Up Visit (Week 16) (\pm 3 days)

- Question the subject about any new or changes in adverse events.
- Question the subject about any new or changes in concomitant medications/therapies.
- Obtain vital signs.
- Obtain a blood sample for immunogenicity testing.
- Perform the Investigators Global Assessment (IGA) of rosacea, the Investigators Assessment of Erythema (IAE) and Other Signs and Symptoms Assessment before performing the lesion count

CONFIDENTIAL

Version Date: 10 July 2015

(refer to Section 7.4.1, 7.4.2, and 7.4.3). **Every effort should be made to maintain consistency of the evaluator for each subject.**

- Perform the inflammatory lesion count (papules and pustules) (refer to Section 7.4.4). **Every effort should be made to maintain consistency of the evaluator for each subject.**

7.4 EFFICACY VARIABLES

The efficacy evaluations should be performed by the Principal Investigator or appropriately qualified Sub-Investigator. The same evaluator should perform the Investigators Global Assessments (IGA), the Investigators Assessment of Erythema (IAEs), Other Signs and Symptoms Assessment and the lesion counts, (see Sections 7.4.1, 7.4.2, 7.4.3, and 7.4.4) for the same subject at each visit. **It is important that the same evaluator performs the Investigator assessments and lesion count for the same subject at each visit, however it may not be feasible in all instances. Every effort should be made to maintain consistency of the evaluator for each subject.**

7.4.1 Investigators Global Assessment (IGA)

The IGA should be performed at screening and each study visit (Baseline, Weeks 1, 3, 6, 9, 12, and 16) prior to performing the lesion count. The IGA is intended for the global evaluation of papulopustular rosacea. Background nontransient erythema and telangiectasias should not be assessed as part of the IGA. The IGA score represents the subject’s condition at the time of the evaluation.

The following categories will be used from the IGA scale to perform the global evaluation of papulopustular rosacea:

Investigators Global Assessment (IGA) Scale

Grade	Grading Scale Score	Description of Papulopustular Rosacea Disease Status
Clear	0	No inflammatory papules or pustules.
Almost clear	1	Very few with 1 or 2 inflammatory papules/pustules.
Mild	2	Several (3-10) small inflammatory papules/pustules.
Moderate	3	11 to 19 small or large inflammatory papules/pustules and no nodules.
Severe	4	Numerous (≥ 20) small and or large inflammatory papules/pustules, and up to 2 nodules, (at baseline).

CONFIDENTIAL

Version Date: 10 July 2015

7.4.2 Investigators Assessment of Erythema (IAE)

The IAE should be performed at screening and each visit (Baseline, Weeks 1, 3, 6, 9, 12, and 16) prior to performing the lesion count using the scale below. The IAE is intended for the global evaluation of erythema of rosacea. This is an assessment of nontransient erythema, or background erythema. Telangiectasias are assessed separately as described under section 7.4.3.

Investigators Assessment of Erythema (IAE) Scale

Grade	Grading Scale Score	Description of Background Erythema
Clear	0	No redness present. Background erythema is consistent with non-involved areas.
Almost Clear	1	Slight and localized background erythema in involved areas of the face, usually limited to the malar prominence of the cheeks. Gives the impression of a healthy glow to the cheeks.
Mild	2	Slight to mild background erythema NOT limited just to the cheeks, but extends to the lateral cheeks, chin, or forehead.
Moderate	3	Definite background redness, easily recognized, and extending to lateral cheeks, chin, or forehead.
Severe	4	Severe background erythema over the entire face.

The IAE rating of erythema is considered as part of the baseline assessment. If a worsening of erythema from Baseline is believed by the investigator to be related to the study drug and not the disease, then it should be recorded as an AE.

7.4.3 Other Signs and Symptoms Assessment

At screening and each study visit (Baseline, Weeks 1, 3, 6, 9, 12, and 16), the investigator must evaluate the severity of the other signs and symptoms of Rosacea. This should be done after evaluating the IGA and IAE, but before performing the lesion count. The areas that will be evaluated are as follows:

- Telangiectasia
- Scaling/peeling
- Pruritus

CONFIDENTIAL

Version Date: 10 July 2015

The score represents that subject's condition at the time of the evaluation. These signs and symptoms will be assessed using the following scales:

Telangiectasia Scale

Grade	Grading Scale Score	Description: Telangiectasia; fine superficial blood vessels that are visible near the surface of the skin.
None	0	No telangiectasias present on the face.
Mild	1	Some to a few telangiectasias are present on the face.
Moderate	2	Many telangiectasias, easily recognized, and extending to lateral cheeks, chin, or forehead.
Severe	3	Many to numerous telangiectasias over the entire face that blends in or matches with the erythema caused by inflammatory lesions. Few matted and dense cluster of vessels present.

Scaling/Peeling Scale

Grade	Grading Scale Score	Description: Scaling/ Peeling
None	0	No evidence of scaling.
Mild	1	Cracks easily evident.
Moderate	2	Marked cracks, wide and deep; scales large and lifting.
Severe	3	Large lifting scales, barely attached or shedding.

Pruritus Scale

Grade	Grading Scale Score	Description: Pruritus
None	0	No itching.
Mild	1	Occasional, slight itching; not really bothersome.
Moderate	2	Constant or intermittent itching that is somewhat bothersome.
Severe	3	Bothersome itching; excoriations of the skin from scratching may be present.

These clinical signs and symptoms of Rosacea: telangiectasia, scaling/peeling and pruritus are considered as part of the baseline and ongoing efficacy evaluation. If a new Rosacea sign or symptom or worsening of a Rosacea sign or symptom is believed by the investigator to be related to the study drug and not the disease, then it should also be recorded as an AE.

CONFIDENTIAL

Version Date: 10 July 2015

7.4.4 Inflammatory Lesion Counts

The area of lesion count assessment is defined as the face from the jaw line to the hairline. The lesion counts will be performed at screening and each study visit (Baseline, Week 1, 3, 6, 9, 12, and 16). The Investigator Global Assessment (IGA), Investigator Assessment of Erythema (IAE) and Other Signs and Symptoms Assessment should be performed prior to performing the lesion count at all visits.

The lesion counts will be performed as follows:

Instructions On Performing Inflammatory Lesion Counts

1. Subjects should have washed their face and removed all makeup at least 15 minutes prior. Male subjects should have already shaved before the study visit.
2. Subjects should be seated at arm's length (or slightly closer) from the evaluator performing the lesion counts and at the same height as the assessor. Subjects should not be seated in direct sunlight.
3. The room should have a balanced and consistent artificial light source or natural light source.
4. The **Principal Investigator or appropriately qualified Sub-Investigators** participating in this study will perform **all** lesion counts. It is essential that the same assessor perform all lesion counts for a given subject for the duration of that subject's participation in the study.
5. Lesions on each area of the face should be considered separately according to the diagram below. Lesions should be counted just to the hairline and no lower than the mandibular line (jaw line). Scan each section of the face systematically from left to right and count only one lesion type at a time. Record each count on the source documents and initial your counts.
6. **ALL LESIONS COUNTED SHOULD BE PALPABLE.** If a lesion is not palpable it should be considered non-active (emerging or resolving). Post-inflammatory lesion pigment changes should not be counted. The inflammatory lesion count includes the total count of papules and pustules, which are defined as follows:

PAPULE – A type of inflammatory lesion; a small erythematous, palpable lesion, usually solid ≤ 0.5 cm in diameter.

[figure not shown]
PUSTULE – A type of inflammatory lesion; a small palpable lesion with an erythematous base approximately 0.5 cm in size and containing pus or yellow-white liquid.

NODULE – A type of inflammatory lesion; a large palpable erythematous papule or plaque that is greater than 0.5 cm in diameter.

Papules should be counted separately from pustules (inflammatory lesions). All lesion types should be counted separately for each quadrant on the face.

CONFIDENTIAL

Version Date: 10 July 2015

Figure 1: Lesion Count Facial Diagram

7.5 SAFETY VARIABLES

7.5.1 Medical/Medication History and Demographics

A medical history including rosacea history, a medication history (including known rosacea treatments used in the last 5 years) will be performed, as well as collection of demographic information at the Screening visit. Medical and medication history will be updated at the Baseline visit. Demographic information will include the subject's age, sex, race, ethnicity and Fitzpatrick skin type (Appendix B). Skin type will be collected based on the subject reported skin type.

7.5.2 Limited Physical Exam and Vital Signs

A limited physical exam will be performed at the Screening Visit (including height and weight) and at the final Week 12 Visit (End of Treatment Visit or Early Termination Visit), including weight will be performed. The limited Physical Exam should include an assessment of the following:

- General Appearance
- Head
- Eyes
- Ears
- Nose
- Throat
- Lungs
- Heart
- Skin

CONFIDENTIAL

Version Date: 10 July 2015

Vital signs (blood pressure, respirations, heart rate) will be measured at the Screening Visit, Week 6, Week 12 (Final or Early Termination) Visit and at the Week 16 (Follow up) Visit.

7.5.3 Clinical Laboratory Testing

Blood samples (approximately 11 mL) will be collected at Screening and the Week 12 Visit (Early Termination, or Final Visit), for hematology and chemistry laboratory analysis (total expected volume of approximately 22 ml). A central laboratory will perform the sample analysis for all study sites. Instructions for sample collection, preparation, labeling, and shipping will be provided by the laboratory.

All laboratory values that are considered clinically significant will be reported as an adverse event and followed as such. The laboratory tests will include the following parameters:

- Hematology: Complete blood count (CBC), including hemoglobin, hematocrit, red blood cell (RBC), white blood cell (WBC), count with differential, and platelet count.
- Blood Chemistry/Lipids: sodium, potassium chloride, bicarbonate or carbon dioxide, glucose, blood urea nitrogen (BUN), creatinine, calcium, uric acid, total bilirubin, total protein, albumin, aspartate aminotransferase (AST), alanine aminotransferase (ALT), alkaline phosphatase, gamma glutamyl transferase (GGT), total cholesterol, high-density lipoproteins (HDL), low-density lipoproteins (LDL), triglycerides, and lactic dehydrogenase (LDH).

7.5.4 Immunogenicity Testing

Blood samples (approximately 6 mL) will be collected at Day 1 (Pre-dose), Week 3, 6, 12 (End of Treatment) and the Post treatment follow-up visit (Week 16) for immunogenicity testing. Samples from all sites will be shipped to a central laboratory and stored prior to sample analysis (total expected volume of approximately 30 mL). Instructions for sample collection, preparation, labeling, and shipping will be provided by the laboratory. It is necessary that the central laboratory has knowledge of the randomization as only samples from subjects who have been randomized to receive omiganan pentahydrochloride topical gel will undergo immunogenicity testing. Sample testing will occur periodically dependent upon an adequate number of samples having been received at the laboratory. Any positive anti-drug antibody test result will be made available following the subject's completion of treatment. It is intended to follow any subjects with positive anti-drug antibody results for up to 1 year from the last study medication use to allow for antibody levels to return to baseline.

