7.5.6 Adverse Event

7.5.6.1 Definition of Adverse Event

An adverse event (AE) is any unfavorable and unintended sign (including a clinically significant abnormal laboratory finding, for example), symptom, or disease temporally associated with the use of a medicinal product, whether or not considered related to the medicinal product. Clinical signs and symptoms of rosacea: erythema, telangiectasia, burning, dryness, scaling/peeling and pruritus are considered as part of the baseline dermatological history. If a new rosacea sign or symptom or worsening of a rosacea sign or symptom is believed by the investigator to be related to the study drug and not the disease, then it should also be recorded as an AE.

At each visit, the study site personnel will question the subject about adverse events using an open question taking care not to influence the subject's answers, e.g., "Have you had any problems since your last visit?"

Any adverse event, whether or not it is related to the test products, will be reported on the source document and eCRF along with the date of onset, the severity, the relationship to the test product and the outcome. Under certain circumstances, additional information may be requested.

When an adverse event persists at the end of the study, the Investigator will ensure a follow-up of the subject until the Investigator/CRO/Sponsor agree that the event is satisfactorily resolved or that no further follow-up is required.

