7.6.4 Unblinding a Subject

This is a double-blind, multicenter study. Subjects will be randomized to once daily treatment with either omiganan topical gel or vehicle. Study drug supplies will be packaged in a manner supporting the blinding of the study.

Unblinding a subject, if needed, will be done through the IWRS. Unblinding a subject's treatment assignment should ONLY be performed in an emergency, when knowing the identity of a subject's assigned treatment is essential to their continuing medical care. If at all possible, every attempt should be made to contact the Medical Monitor to discuss this before opening the blinded panel to determine the subject's treatment assignment. The contact information for the Medical Monitor's is provided on the front page of the protocol. In the event of unblinding, the Medical Monitor and Project Manager must be notified immediately (within 24 hours(1 business day)), and the circumstances under which the code for a given subject was broken must be documented in the subject's eCRF.

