7.7.3 Randomization

Subjects providing written informed consent and having met all inclusion and exclusion criteria will be randomized to 1 of 2 treatment groups in a 1:1 ratio, according to a predetermined computer-generated randomization code.

CONFIDENTIAL

Version Date: 10 July 2015

Subjects will be randomized to treatment using an Interactive Web Response System (IWRS). The randomization scheme will include investigative site. The randomization will be performed using permuted blocks.

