7.7.4 Analysis Populations

The 'Intent-to-treat' (ITT) analysis population will include all randomized subjects. The ITT population will be the primary population for all efficacy analyses.

The "All-treated" analysis population will consist of all subjects receiving at least one application of study medication. All safety analyses will be performed on the all-treated population.

The Per-Protocol (PP) population will include all subjects in the ITT population who provide Baseline and Week 12 efficacy data for all primary endpoints and complete the 12-week treatment period without any major deviations from the protocol.

The subjects to be included in the PP analysis population will be determined by the Sponsor/CRO prior to the unblinding of the study. The PP population will be secondary for the co-primary endpoints only.

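### A released anti-drug antibody positive identifies the omiganan arm and may be released before that subject's Week 16 scoring

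*Protocol*

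**What the plan says.** Protocol 7.5.4 collects immunogenicity samples before dosing on Day 1, at Weeks 3, 6 and 12, and at Week 16. It labels Week 12 as the end of treatment. Blood is taken from every subject, but the laboratory is given the randomization because "only samples from subjects who have been randomized to receive omiganan pentahydrochloride topical gel will undergo immunogenicity testing".

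Three further statements in the same section matter here:

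- On timing of the assay: "Sample testing will occur periodically dependent upon an adequate number of samples having been received at the laboratory".
- On release: "Any positive anti-drug antibody test result will be made available following the subject's completion of treatment". The trigger is the individual subject's end of treatment. It is not database lock or study unblinding, and no recipient is named.
- On what follows a positive: "It is intended to follow any subjects with positive anti-drug antibody results for up to 1 year from the last study medication use".

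Elsewhere, Protocol 7.6.4 says that unblinding a subject's "treatment assignment should ONLY be performed in an emergency", through the IWRS and with documentation. It does not mention antibody results. Protocol 7.1 gives assessment of relapse as the purpose of the four-week follow-up. Protocol 7.3.2.5 repeats the IGA, the erythema assessment, the other signs and symptoms and the lesion count at Week 16, and asks about adverse events. Under Protocol 7.5.6.1, a new or worse rosacea sign is also recorded as an adverse event if it is "believed by the investigator to be related to the study drug and not the disease". The SAP does not address the handling or blinding of antibody results.

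**The concern.** With one arm tested, the existence of a positive result discloses the assignment, whatever the assay shows about antibodies. The release rule therefore creates a second way of learning a subject's arm, which 7.6.4 neither covers nor documents.

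Two kinds of data depend on investigator judgment after the release point. One is the Week 16 scoring used to describe relapse. The other is the judgment, for events in the follow-up period, of whether a change in the skin is due to the drug or the disease. Knowledge of assignment could arise this way in omiganan subjects only, so any effect on scoring or attribution would fall on one side of the comparison. The planned extended follow-up of positives adds to this: if it were arranged with the subject before Week 16, the arrangement would itself signal the arm.

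**Working it through.** The plan gives no figure on this point to reproduce. The check is whether a positive identifies the arm, whether release can precede Week 16 scoring, and how many subjects might be involved.

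**1. What a released positive reveals.** Inputs: 1:1 allocation (Protocol 7.7.3) and testing of omiganan samples only (7.5.4). Let s be the positivity rate on omiganan. Vehicle contributes zero because it is not tested.

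P(omiganan | positive released) = 0.5s / (0.5s + 0.5 × 0) = 1, for any s above zero.

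This certainty comes from the one-arm testing. If both arms were tested with assumed rates of 5% on omiganan and 1% on vehicle, the value would be 0.025 / (0.025 + 0.005) = 0.83.

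**2. Time between permitted release and Week 16 scoring.** Inputs: Week 12 = day 84, Week 16 = day 112, each ± 3 days (Protocol 7.3.1, 7.3.2.4, 7.3.2.5).

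- Nominal: 112 − 84 = 28 days.
- Shortest: (112 − 3) − (84 + 3) = 22 days.
- Longest: (112 + 3) − (84 − 3) = 34 days.

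How likely release is within this interval depends on the sample:

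- Day 1, Week 3 and Week 6: the assay may already be done when treatment ends, because testing is periodic, and the result could then be released at once.
- Week 12: shipping, storage, batching and assay must all fit within the 22 to 34 days. No turnaround time is given.
- Week 16: a first positive on this sample cannot affect that visit's scoring.

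**3. How many subjects.** The documents give no positivity rate. Assumed rates applied to the 225 planned omiganan subjects (Protocol 7.7.2):

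| Assumed positivity | Calculation | Identifiable omiganan subjects | Vehicle |
|---|---|---|---|
| 2% | 225 × 0.02 = 4.5 | about 5 | 0 |
| 5% | 225 × 0.05 = 11.25 | about 11 | 0 |
| 10% | 225 × 0.10 = 22.5 | about 23 | 0 |

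These are upper figures for each rate. They count all positives, whether or not the result arrives before Week 16, and SAP 5.4.2 records that enrollment was discontinued after the interim analysis. Protocol 5.1 reports no systemic absorption, which does not exclude antibodies but is relevant to the choice of range.

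**4. Which data come before and after release, for a subject who completes 12 weeks.**

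| Data | Relative to release of that subject's result |
|---|---|
| Week 12 co-primary scores | Before |
| Adverse events assessed at visits through Week 12 | Before |
| Week 16 IGA, erythema, signs and symptoms, lesion count | Possibly after |
| Attribution of adverse events in the follow-up period | Possibly after |

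**The case against.** The strongest objection is that Week 16 may not be meant to be blinded. Both documents attach the term double-blind to the 12-week treatment period: Protocol 7.2.3 contrasts it with the follow-up period, Protocol 7.7.11 speaks of a double-blind portion, and SAP 2.0, 3.0 and 5.4.4 use similar language. Release at the end of treatment could then be a deliberate hold that protects the co-primary endpoints. This stands as a real ambiguity. Against it, no unblinding is planned at Week 12, 7.6.4 allows only emergency unblinding, and unblinding is otherwise treated as a study-level event. The per-protocol set, for instance, "will be determined by the Sponsor/CRO prior to the unblinding of the study". Blinding at Week 16 is thus a reasonable inference but not a stated fact.

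The second objection is that harm needs a chain of events: a positive result, reporting before Week 16, and delivery to the person who scores. That also stands. Receipt by the site is not stated, and part of Protocol 7.6 is missing from the text available, so the absence of a named recipient can be asserted only for what is visible.

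Third, a reader might infer that the co-primary endpoints are compromised. The documents do not support this for completers, whose Week 12 scores precede release. For early stoppers, Protocol 7.2.3 calls for the Week 12 procedures at stopping, and 7.5.2 treats an early termination visit as equivalent. What is left open is whether stopping early counts as completing treatment for a subject who continues to attend visits.

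Fourth, a reader might infer that one revealed subject lets staff work out others at the site, since "The randomization scheme will include investigative site. The randomization will be performed using permuted blocks". That requires a known block size and known block boundaries. The documents give neither, so no figure can be supported.

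**Conclusion.** The point holds as a minor weakness in the blinding arrangements. Protocol 7.5.4 permits a result that identifies the arm with certainty to be released 22 to 34 days before the Week 16 visit, outside the route in 7.6.4 and in the omiganan arm only. It does not require or guarantee this.

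The data exposed are the Week 16 efficacy summaries and the follow-up adverse events. The former are descriptive (Protocol 7.7.13, SAP 5.4.5), the latter are summarized separately (SAP 5.4.4), and SAP 5.4.2 treats all analyses as exploratory. Nothing here undermines a completer's own co-primary or on-treatment safety data.

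The conclusion that scoring could be affected rests on two inferences: that the result may reach the site, and that Week 16 is meant to be scored blind. The 5 to 23 subjects rest on assumed positivity of 2% to 10% and full planned enrollment.

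**What to change.** Change the release point in Protocol 7.5.4. Suggested content: *A positive antibody result is released only once that subject's Week 16 assessments are recorded or, where there is no Week 16 visit, once the last study assessment is recorded. Until then it stays with the central laboratory or a named recipient independent of the evaluators.* Tying release to recorded assessments also settles the position of early stoppers.

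Three clarifications should go with it:

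- State whether Week 16 is scored blind.
- Reconcile 7.5.4 with 7.6.4, including how an earlier need for a result would be handled.
- Reconcile 7.5.4 with the planned follow-up of positives for up to 1 year, so that its start is compatible with the later release.

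The cost is a short edit to 7.5.4 and to the laboratory instructions. No extra testing is needed, because the laboratory already holds the randomization. The downside is that routine release comes about 4 weeks later (22 to 34 days with visit windows), on results that the protocol already withholds throughout treatment. A hold until study unblinding is not recommended: it could take up much of the planned follow-up year, by an amount that cannot be calculated because the study dates are redacted.
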